1.1 Background and rationale

Overuse injuries are common among competitive Norwegian rhythmic gymnasts with a mean weekly prevalence of 37% [95% CI: 36% to 39%] and incidence of 4.2 new overuse injuries [95% CI: 3.6 to 4.9] per gymnast per year (Gram, M., Clarsen, B., & Bø, K., 2021). The knees, lower back and hip/groin were the most common injury locations. It has been postulated that reduced physical capacity (e.g strength, flexibility, stability) in the knees, lower back and hip/groin can increase the risk of injuries in rhythmic gymnastics.

In addition, more than 30% of the Norwegian rhythmic gymnasts experience urinary incontinence (UI), and 70% reported that UI negatively affected sports performance (Gram, M., & Bø, K., 2020). Few of the rhythmic gymnasts had any knowledge about the pelvic floor.

Hence, this assessor blinded cluster randomized controlled trial aims to find out whether the implementation of exercises targeting reduced physical capacity and pelvic floor dysfunction can prevent/reduce the prevalence of overuse injuries and UI.

The results from this RCT will be presented in two separate publications: **Publication I** on overuse injuries and **Publication II** on UI.

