1.2.2 Secondary Objectives

Publication I: The secondary objectives are:

- I. To assess if implementation of exercises targeting reduced capacity in the lower back, knees and hip/groin reduces the prevalence of substantial overuse injuries in these areas compared with no targeted intervention.
- II. The primary objective and the secondary objective number I) including overuse injuries in the calf/ankle/foot in addition to lower back, knees and hip/groin.
- III. To assess the self-experienced effect and progress of the exercise program related to overuse injuries in the knees, lower back and hip/groin in the intervention group.

STATISTICAL ANALYSIS PLAN for NCT05506579

Publication II: The secondary objectives are:

- I. To assess if implementation of PFMT reduces the prevalence of UI compared with no targeted intervention.
- II. The primary objective and the secondary objective number I) but restricted to gymnasts having UI.
- III. The primary objective and the secondary objective number I) but restricted to gymnasts having SUI.
- IV. To assess the self-experienced effect and progress of the exercise program related to UI in the intervention group.

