2.3 Sample size

The power calculation for Publication I (overuse injuries) is based on average prevalence in our previous study (Gram, M., Clarsen, B., & Bø, K., 2021) and previous studies with a

STATISTICAL ANALYSIS PLAN for NCT05506579

similar design (Olsen, et.al, 2005). With 80% power, 5% significance level and a decrease in the primary outcome measure from 40% to 20% in the intervention group and no change in the control group at least 158 gymnasts are required. In addition, to account for randomization at the cluster level, the total number were multiplied with an inflation factor (DE) of 1.4 (based on the following assumptions; average number of gymnasts per club (cluster) $m = 9$, $ICC = 0.05$, $DE = 1+(m - 1)*ICC = 1+(9 - 1)*0.05 = 1.4$), resulting in a required total sample size of 220 gymnasts (110 in each group).

The power calculation for Publication II (UI) is based on average prevalence in our previous study (Gram, M., & Bø, K., 2020) and studies with a similar design (Ferreira, et.al, 2014). With 80% power, 5% significance level and a decrease in the total sum score of ICIQ from 4.7 to 2.5 (SD 2.1) in the intervention group and no change in the control group at least 30 gymnasts are required. Multiplied with the same DE, the total required sample size will be 42 gymnasts (with 21 in each group).

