3.3 Analysis Populations

The Enrolled set will include all gymnasts who have provided informed consent and have been included into the study data base.

The Full Analysis Set (FAS) will be defined as all gymnasts randomly assigned to either the intervention or control group and who have responded to:

STATISTICAL ANALYSIS PLAN for NCT05506579

- Publication I: The OSTRC-H2 questionnaire either at baseline (Oct 2022) or Nov 2022 + one or more of April, May and June 2023.
- Publication II: The ICIQ-UI-SF questionnaire at baseline and in June 2023.

The Per Protocol Analysis Set (PPS) will include all randomised gymnasts meeting the study eligibility criteria and with no major protocol deviations affecting the intervention efficacy (FAS + completed 65% or more of the intervention sessions per week).

4 Trial Population

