5.1 Outcome Definitions

All outcomes will be analyzed on the full analysis set. An additional analysis of the primary outcome (in both publications) and the secondary outcomes I) (publication I) and I)-III) (publication II) will be performed on the per protocol set.

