5.1.1 Primary Outcome Definition

Publication I: The primary outcome is the prevalence of overuse injuries in the lower back, knees and hip/groin during the intervention period. In the OSTRC-H2 a health problem is defined as: “any condition that you consider to be a reduction in your normal state of full health, irrespective of its consequences on your sports participation or performance, or whether you have sought medical attention. This may include, but is not limited to, injury, illness, pain or mental health conditions.” Furthermore, an overuse injury is defined as: “an injury caused by multiple accumulative bouts of energy transfer without a single, clearly identifiable event responsible for the injury.” (Clarsen, et.al, 2020; Clarsen, et.al 2014). The primary outcome is dichotomous.

Publication II: The primary outcome is the bother of UI before and after the intervention period. Degree of bother is defined with the ICIQ-UI-SF sum score (0-21 points). The primary outcome is continuous.

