5.1.4 Overview of Outcomes Publication II

Level	Outcome	Timeframe	Type
Primary	Bother of UI	Baseline (Oct 2022) + after intervention (June 2023)	Continuous
Secondary	Prevalence of UI	Baseline (Oct 2022) + after intervention (June 2023)	Dichotomous
	Bother and prevalence of UI restricted to gymnasts having UI	Baseline (Oct 2022) + after intervention (June 2023)	Continuous / Dichotomous
	Bother and prevalence of UI restricted to gymnasts having SUI	Baseline (Oct 2022) + after intervention (June 2023)	Continuous / Dichotomous
	Self-experienced effect and progress	After intervention (June 2023)	Continuous
Sub-group analysis	Bother and prevalence of UI for all gymnasts training less or more than 15 hours per week	Baseline (Oct 2022) + after intervention (June 2023)	Continuous/ Dichotomous
	Bother and prevalence of UI restricted to gymnasts having UI training less or more than 15 hours per week	Baseline (Oct 2022) + after intervention (June 2023)	Continuous/ Dichotomous
	Bother and prevalence of UI restricted to gymnasts having SUI training less or more than 15 hours per week	Baseline (Oct 2022) + after intervention (June 2023)	Continuous/ Dichotomous

STATISTICAL ANALYSIS PLAN for NCT05506579

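### The 42 gymnasts required for Publication II come from ICIQ inputs that fit mainly incontinent gymnasts, while the primary analysis covers all gymnasts

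*SAP*

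**What the plan says.** Section 2.3 assumes a "decrease in the total sum score of ICIQ from 4.7 to 2.5 (SD 2.1) in the intervention group", no change in the control group, 80% power and a 5% level. This gives 30 gymnasts. Then: "Multiplied with the same DE, the total required sample size will be 42 gymnasts (with 21 in each group". The design effect is the 1.4 derived for Publication I (m = 9, ICC = 0.05). The stated basis is an average prevalence from the group's previous study plus studies of similar design, although the inputs are score means. Neither the population nor the type of SD is given.

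The primary outcome is the score itself: "Degree of bother is defined with the ICIQ-UI-SF sum score (0-21 points". The full analysis set for Publication II (3.3) asks only for "The ICIQ-UI-SF questionnaire at baseline and in June 2023", and section 5.1 adds: "All outcomes will be analyzed on the full analysis set". The ANCOVA in 5.2.2 has no UI condition.

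The UI-only analysis is a separate secondary objective (1.2.2, item II): "The primary objective and the secondary objective number I) but restricted to gymnasts having UI". Section 1.2.3 plans a training-load subgroup analysis of the primary outcome, and the matching row in 5.1.4 reads "Bother and prevalence of UI for all gymnasts training less or more than 15 hours per week". The primary analysis is therefore unrestricted. On prevalence, section 1.1 says "more than 30% of the Norwegian rhythmic gymnasts experience urinary incontinence (UI".

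**The concern.** A score that is zero or near zero for most of the sample has a low mean, an SD that is large relative to that mean, and a treatment difference diluted by everyone who has nothing to improve. A mean of 4.7 with an SD of 2.1 does not look like such a score. It looks like the score among gymnasts who leak. If so, the standardised effect of 2.2/2.1 = 1.05 belongs to the secondary UI-only analysis, and the primary analysis has no sample-size justification of its own. A reader who takes 42 as the requirement could judge the number of gymnasts with both questionnaires to be ample when it is not.

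**Working it through.** **1. The plan's figure.** n per arm = 2 × (1.96 + 0.8416)² × 2.1² / 2.2² = 14.3, rounded up to 15. Total 30; 30 × 1.4 = 42. The arithmetic is right.

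**2. Do the inputs fit all gymnasts?** Assume gymnasts without UI score 0.
- Mean needed among those with UI for an overall 4.7: 4.7/0.30 = 15.7 at 30% UI; 4.7/0.40 = 11.75 at 40%. The scale maximum is 21.
- Drop needed among them for an overall 2.2, if only they improve: 2.2/0.30 = 7.3; 2.2/0.40 = 5.5.
- If 2.1 is a cross-sectional SD and a share p scores above 0, then SD ≥ 4.7 × √((1−p)/p). Setting this to 2.1 gives p ≥ 0.834. At least 83% would have to score above 0. This bound needs no prevalence or correlation assumption.

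**3. What 42 gives for the all-gymnast ANCOVA.** These are illustrations, not replacement values. Assumptions not in the SAP: gymnasts without UI score 0; those with UI have mean 4.7, or 2.5 under treatment, SD 2.1; design effect 1.4 still applies. Let p be the UI share, k the share of UI persisting from October to June at constant prevalence, and r the within-UI correlation.

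- Difference = 2.2p: 0.66 at 30%, 0.88 at 40%.
- var(Oct) = var(June, control) = 2.1²p + 4.7²p(1−p): SD 2.44 or 2.66. Standardised effect 0.66/2.44 = 0.27 or 0.88/2.66 = 0.33.
- var(June, intervention) = 2.1²p + 2.5²p(1−p).
- cov(control) = pk(2.1²r + 4.7²) − 4.7²p²; cov(intervention) = pk(2.1²r + 4.7×2.5) − 4.7×2.5×p².
- Common slope b = mean covariance / var(Oct). Residual variance per arm = var(June) − 2b·cov + b²·var(Oct).
- n per arm = 7.849 × (sum of residual variances) / (2.2p)²; total = 2 × 1.4 × n.

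Example, p = 0.30, k = 1, r = 0.5: var(Oct) 5.96; covariances 5.30 and 3.13; b = 0.707; residual variances 1.447 and 1.191; n = 7.849 × 2.638 / 0.4356 = 47.5; total 133.

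If 2.1 is instead an SD of change among those with UI, the change variances are 2.1²p (control) and 2.1²p + 2.2²p(1−p) (intervention).

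| Scenario | UI share | Required total | Power with 42 | Power with 220 |
|---|---|---|---|---|
| UI stable, r = 0 to 0.7 | 30% | 220 to 94 | 23–46% | 80–99% |
| | 40% | 161 to 68 | 30–60% | 91–99.9% |
| 2.1 is an SD of change | 30% | 185 | 27% | 86% |
| | 40% | 133 | 35% | 95% |
| 70–85% of UI persists, r = 0 to 0.7 | 30% | 217–364 | 16–23% | 59–81% |
| | 40% | 158–260 | 20–30% | 73–91% |

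Section 1.1 gives no upper limit for prevalence. At 50% UI the three scenarios together need 52–195, with power 25–71% at 42 and at least 84% at 220. With stable UI, 42 reaches 80% power only at a UI share of about 60% (r = 0.7), 80% (r = 0.5) or 99% (r = 0).

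**4. If 42 means gymnasts with UI.** Expected numbers with UI are 0.30 × 220 = 66 and 0.40 × 220 = 88, giving 95% and 99% power at design effect 1.4, before losses. With only gymnasts with UI analysed, m = 9p = 2.7 or 3.6, so the design effect is 1.085 or 1.13 and the 30 becomes 33–34 rather than 42. But 42 enrolled would contain only about 13–17 with UI.

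**The case against.** The strongest reply is that 42 governs nothing. The same gymnasts serve both publications, Publication I requires 220, and at 30–40% UI the power at 220 is at least 80% in the stable-UI and SD-of-change scenarios. It falls below 80% only when incomplete persistence of UI is assumed, for which the SAP gives no figure. That stands: underpowering of the trial is not shown, and no estimate, test or decision rule changes. But the SAP never ties 220 to Publication II. It presents 42 as that publication's requirement.

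It is also fair that the population behind 4.7, 2.5 and 2.1 is inferred. The 83% bound needs a cross-sectional SD, and the 15.7 and 11.8 need continent gymnasts to score about 0. The required sizes move a good deal with the assumptions: at 30% UI, a cruder calculation that uses the control-arm SD in both arms and a free overall correlation of 0.5 to 0.8 gives 454 to 219. So no single replacement number can be read off. All of these calculations agree, however, that 42 is too few at 30–40% UI.

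Finally, section 2.5 describes the assessments in the past tense, so a new calculation would be retrospective. That is a reason to label it as such and keep the planning calculation visible, not a reason to leave 42 attached to the wrong analysis.

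**Conclusion.** The concern holds. The calculation is arithmetically correct but does not support the analysis to which it is attached. Under any of the mixtures examined at 30–40% UI, 42 gymnasts give 16–60% power for the primary ANCOVA instead of 80%, and the required total is 68 to 364. These figures rest on continent gymnasts scoring 0, benefit only among those with UI, and a design effect of 1.4. The consequence is limited to the stated justification: the planned confidence interval will still show the precision achieved, and 220 may well be enough. It should be corrected because it is the only sample-size statement for one of the two primary outcomes.

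**What to change.** In section 2.3:
- State which gymnasts the 4.7, 2.5 and 2.1 describe, and whether 2.1 is a cross-sectional SD or an SD of change.
- If they describe gymnasts with UI, assign that calculation to secondary outcome II, count the result in gymnasts with UI, and set m to the number of gymnasts with UI per club.
- For the primary outcome, replace 42 with the required size and the power at 220 for the all-gymnast ANCOVA. Declare the assumed UI prevalence, mixture SD, October–June correlation and persistence of UI, and mark the text as added after the assessments.
- Leave the primary population as it is, since the assessments are described as done.

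The cost is one recalculation and one rewritten paragraph, with a less favourable stated figure that depends on declared assumptions. Population, test and enrolment do not change.

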2.4 Statistical Framework

2.4.1 Hypothesis Test

This RCT is designed to establish superiority of the intervention.

Publication I:

- The primary null hypothesis is that the prevalence of overuse injuries in the lower back, knees and hip/groin in the intervention group is the same as the prevalence of overuse injuries in the lower back, knees and hip/groin in the control group.
- The alternative hypothesis corresponding to the primary null hypothesis is that the prevalence of overuse injuries in the lower back, knees and hip/groin in the intervention group is lower or higher than the prevalence of overuse injuries in the lower back, knees and hip/groin in the control group.

There is only one identified primary analysis in this publication. All other efficacy analyses will be regarded as supportive or exploratory.

Publication II:

- The primary null hypothesis is that the bother of UI in the intervention group is the same as the bother of UI in the control group.
- The alternative hypothesis corresponding to the primary null hypothesis is that the bother of UI in the intervention group is less or more than the bother of UI in the control group.

There is only one identified primary analysis in this publication. All other efficacy analyses will be regarded as supportive or exploratory.

STATISTICAL ANALYSIS PLAN for NCT05506579

2.4.2 Decision Rule

This RCT is designed to address a single primary outcome for each publication. Superiority of the intervention is claimed if the primary null hypothesis is rejected on the significance level (alpha) of 0.05 (two-sided).

2.5 Timing of Outcome Assessments

Publication I:

- Primary outcome: To assess the prevalence of overuse injuries in the lower back, knees and hip/groin, the Oslo Sports Trauma Research Center Questionnaire on Health Problems (OSTRC-H2) was used. The gymnasts in both groups answered the OSTRC-H2 at baseline (October 2022) and one time each month (last Sunday during the month) throughout the intervention period (November 2022 - June 2023).
- Secondary outcome:
 - I. To assess the prevalence of substantial overuse injuries in the lower back, knees and hip/groin, the same assessment method and time frame as listed above for the primary outcome was used.
 - II. To assess the primary outcome and the secondary outcome number I) including overuse injuries in the calf/ankle/foot in addition to lower back, knees and hip/groin, the same assessment method and time frame as listed above for the primary outcome was used.
 - III. To assess self-experienced effect and progress of the exercise program related to overuse injuries in the knees, lower back and hip/groin, a global rating of change (GRC) 11-point numerical scale was used. The gymnasts in the intervention group answered the GRC one time when the intervention period had ended (June 2023).

Publication II:

- Primary outcome: To assess the bother of UI, The International Consultation on Incontinence Questionnaire - Urinary Incontinence Short Form (ICIQ-UI-SF) was used. The gymnasts in both groups answered the ICIQ-UI-SF one time at baseline (October 2022) and one time when the intervention period had ended (June 2023).
- Secondary outcome:
 - I. To assess the prevalence of UI, the same assessment method and time frame as listed above for the primary outcome was used.
 - II. To assess the primary outcome and the secondary outcome number I) restricted to gymnasts having UI, the same assessment method and time frame as listed above for the primary outcome was used.
 - III. To assess the primary outcome and the secondary outcome number I) restricted to gymnasts having SUI, the same assessment method and time frame as listed above for the primary outcome was used.
 - IV. To assess self-experienced effect and progress of the exercise program related to UI, a global rating of change (GRC) 11-point numerical scale was used. The gymnasts in the intervention group answered the GRC one time when the intervention period had ended (June 2023).

STATISTICAL ANALYSIS PLAN for NCT05506579

Subgroup analysis variable: Weekly training load (hours/week) was reported by the gymnasts in the baseline questionnaire (October 2022).

3 Statistical Principles

3.1 Confidence Intervals and p-values

All calculated p-values will be two-sided and compared to a 5% significance level. If a p-value is less than 0.05, the corresponding group difference will be denoted as statistically significant. All efficacy estimates will be presented with two-sided 95% confidence intervals. As there is only one primary null hypothesis to be tested per publication, there will be no adjustments for multiplicity.

3.2 Adherence and Protocol Deviations

3.2.1 Adherence to Allocated Intervention

Adherence is assessed based on the percent of gymnasts who have conducted 65% or more of the required intervention sessions per week:

% adherence = (mean number of completed intervention sessions per week / number of weekly RG training sessions) *100%.

The number of weekly RG training sessions will be calculated based on training load stated in the baseline questionnaire (weekly hours of training / 3 hours (average length of an RG training)).

The number and % of gymnasts performing 65% or more of the required intervention sessions per week will be presented.

3.2.2 Protocol Deviations

The following are pre-defined major protocol deviations regarded to affect the efficacy of the intervention:

- Discontinuation of conducting weekly intervention sessions (adherence <65%, see more details in 3.2.1)

The number and % of gymnasts with major protocol deviations will be stated in the publications.

3.3 Analysis Populations

The Enrolled set will include all gymnasts who have provided informed consent and have been included into the study data base.

The Full Analysis Set (FAS) will be defined as all gymnasts randomly assigned to either the intervention or control group and who have responded to:

STATISTICAL ANALYSIS PLAN for NCT05506579

- Publication I: The OSTRC-H2 questionnaire either at baseline (Oct 2022) or Nov 2022 + one or more of April, May and June 2023.
- Publication II: The ICIQ-UI-SF questionnaire at baseline and in June 2023.

The Per Protocol Analysis Set (PPS) will include all randomised gymnasts meeting the study eligibility criteria and with no major protocol deviations affecting the intervention efficacy (FAS + completed 65% or more of the intervention sessions per week).

4 Trial Population

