4.1 Screening Data, Eligibility and Recruitment

The total number of invited clubs (with their gymnasts) and reasons for not entering the RCT will be summarised and tabulated.

A CONSORT flow diagram will be used to summarise the number of rhythmic gymnastics clubs/gymnasts who were:

- assessed for eligibility at screening (all rhythmic gymnastics clubs in Norway)
- eligible at screening (all rhythmic gymnastics clubs in Norway having gymnasts ≥ 12 years of age training ≥ 3 days per week)
- ineligible at screening*
- eligible and randomised (including number of gymnasts per club)
- eligible but not randomised* (including number of gymnasts per club)
- received the randomised allocation (including number of gymnasts per club)
- did not receive the randomised allocation* (N/A)
- lost to follow-up*
- discontinued the intervention*
- randomised and included in the primary analysis
- randomised and excluded from the primary analysis*

*reasons will be provided.

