5.2 Analysis Methods

5.2.1 Publication 1

The outcomes prevalence of overuse injuries (primary outcome) and prevalence of substantial overuse injuries (secondary outcome) will be analyzed with multilevel mixed effect logistic regression models. The models will be fitted with outcome data from all time points (Nov, Dec, ..., June) except the baseline (Oct). The models will have a fixed effect for group (intervention vs control) and two random intercepts: gymnast and club, with gymnast nested within club. Based on the fitted model, we will present the odds ratio (OR) for injury (with 95% confidence interval [CI]) for intervention vs control and the P-value for the null hypothesis of an OR = 1.

The observed prevalence of injuries (with 95% CI) for each time point (Oct, Nov, ..., June) for the primary outcome and the secondary outcome I) and II) will be presented in a figure.

Self-experienced effect and progress is measures on a -5 to 5 scale and only measured after end of the intervention (June) and only for the gymnasts in the intervention group. We will present the observed number and percentage of responses in each category (-5, -4, ..., 4, 5) and also the mean and standard deviation of the responses.

5.2.2 Publication 2

Bother of UI (primary outcome) at the end of the intervention (June) will be analyzed with linear regression, with the June measurement as the dependent variable and group (intervention vs control) and the baseline (Oct) measurement as independent variables (ANCOVA). The standard errors in the model will be adjusted for the clustering of gymnasts within clubs. We will present the mean and standard deviation of the baseline and end-of-intervention measurements for each group and the estimated between-group difference in changes from baseline to end-of-intervention with a 95% CI. We will also give the P-value for the null hypothesis of a zero between-group difference.

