5.2.3 Sensitivity analyses

A sensitivity analysis of the prevalence of injuries (primary outcome in publication 1) will be performed with a mixed effect logistic regression model where only the June measurement is used as an outcome. The model will have a fixed effect for group (intervention vs control) and a random intercept for club to account for the clustering of gymnasts within clubs.

STATISTICAL ANALYSIS PLAN for NCT05506579

A sensitivity analysis of the bother of UI (primary outcome in publication 2) will be performed with a quantile (median) regression model with the June measurement as dependent variable and group (intervention vs control) and the baseline (Oct) measurement as independent variables.

6 Statistical Software

All statistical analyses will be done in Stata version 17 (StataCorp LLC, College Station, TX, USA).

7 References

Clarsen, B., et al., *The Oslo Sports Trauma Research Center questionnaire on health problems: a new approach to prospective monitoring of illness and injury in elite athletes*. British journal of sports medicine, 2014. 48(9): p. 754-760.

Clarsen, B., et al., *Improved reporting of overuse injuries and health problems in sport: an update of the Oslo Sport Trauma Research Center questionnaires*. British Journal of Sports Medicine, 2020. 54(7): p. 390-396.

Ferreira, S., et al., Reeducation of pelvic floor muscles in volleyball athletes. Revista da Associação Médica Brasileira, 2014. 60(5): p. 428-433

Olsen, O.-E., et al., Exercises to prevent lower limb injuries in youth sports: cluster randomised controlled trial. BMJ, 2005. 330(7489): p. 449.

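### The Publication I full analysis set requires an early and a late questionnaire that the primary model does not need, so valid November–June outcomes are discarded on a post-randomisation retention rule

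*SAP*

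**What the plan says.** Section 3.3 starts the FAS from "all gymnasts randomly assigned to either the intervention or control group" and then adds a response condition. For Publication I the condition is "The OSTRC-H2 questionnaire either at baseline (Oct 2022) or Nov 2022 + one or more of April, May and June 2023".

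Section 5.1.1 defines the outcome over the whole trial period: "The primary outcome is the prevalence of overuse injuries in the lower back, knees and hip/groin during the intervention period". Section 5.2.1 describes the data for the primary model: "The models will be fitted with outcome data from all time points (Nov, Dec, ..., June) except the baseline (Oct"). Group is the only fixed effect, with random intercepts for club and for gymnast within club.

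Section 5.1 states: "All outcomes will be analyzed on the full analysis set". The per-protocol set in section 3.3 is the FAS with an adherence condition added, so it is a subset. The Enrolled set is defined but no analysis uses it. The one sensitivity analysis of this outcome, in section 5.2.3, is "a mixed effect logistic regression model where only the June measurement is used as an outcome". Section 4.1 will report, with reasons, the gymnasts "randomised and excluded from the primary analysis".

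**The concern.** The set and the model do not fit each other. The outcome covers eight months and the model can use any of them, yet entry to the analysis depends on answering in two particular windows. The April–June window lies five months or more into the intervention, so inclusion depends on retention after randomisation.

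This affects the only primary analysis of Publication I. Precision is lost whatever the reason for non-response. If continued response is related to injury, the odds ratio can be biased as well. A link between response and allocation is conceivable, because only one arm is asked to do extra exercises.

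The sentence in section 3.3 also has no brackets. It can be read as October alone, or November plus a late response. On that reading, gymnasts with an October answer and no outcome at all enter the set.

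**Working it through.** **Plan's own figure.** Section 2.3 assumes "a decrease in the primary outcome measure from 40% to 20% in the intervention group" with 80% power and 5% significance. The unpooled formula gives (1.960 + 0.842)² × (0.40×0.60 + 0.20×0.80) / 0.20² = 78.5, so 79 per arm and 158 in total, as stated. With the design effect, 158 × 1.4 = 221.2 against 220 stated. The sample size is not in dispute, but no dropout allowance is stated in it.

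**Which response patterns are lost.** There are nine questionnaires (October, then November to June). Patterns with at least one usable outcome: 2 × (2⁸ − 1) = 510.
- Natural reading, (October or November) and (April, May or June): 3 × 2⁴ × 7 = 336 kept, 174 excluded.
- Second reading, October or (November and a late response): of the 255 usable patterns without October, 2⁴ × 7 = 112 are kept and 143 excluded.

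These are counts of patterns, not expected proportions.

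**Data loss (response rates are assumptions; the SAP gives none).**

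*Dropout.* All answer October and November, then a share h stops each month. Gymnasts excluded = 1 − (1−h)⁵. Outcome months lost = Σₖ₌₁..₅ k·h·(1−h)ᵏ⁻¹, divided by months recorded, (1 − (1−h)⁸)/h.

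| h | Gymnasts excluded | Outcome months lost |
|---|---|---|
| 2% | 9.6% | 0.284/7.462 = 3.8% |
| 5% | 22.6% | 0.655/6.732 = 9.7% |
| 8% | 34.1% | 0.966/6.085 = 15.9% |

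*All stopping just after March.* For a share s, the loss is 5s/(5s + 8(1−s)): 6.5% at s = 10% and 21.1% at s = 30%.

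*Scattered non-response only.* Each questionnaire is missed with probability q. The loss is (7q² + 5q³ − 4q⁵)/8: 0.9%, 4.0% and 9.4% at q = 10%, 20% and 30%.

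*Both readings, mixed case.* With 90% answering each questionnaire and 5% monthly dropout, 10.9% of outcome months are lost on the natural reading. On the second reading the loss is 1.8%, and 0.5% of gymnasts enter with no outcome.

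**Precision and bias (simulation).** Inputs from section 2.3 are 9 gymnasts per club, ICC 0.05 and 40% against 20%. Assumed: gymnast SD 2 on the logit scale. An ICC of 0.05 on the latent scale then gives a club SD of √(0.05/0.95 × (4 + π²/3)) = 0.62. With these SDs, 40% against 20% is a conditional odds ratio of 0.201. The planned model was fitted to 4,000 clubs per arm, once with all responses and once with the FAS. Standard errors are scaled to 25 clubs (220/9 = 24.4).

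Effective sample size lost = 1 − (SE all / SE FAS)²:
- 2% monthly dropout: 1 − (0.399/0.407)² = 4%
- 5%: 1 − (0.404/0.430)² = 12%
- 8%: 1 − (0.409/0.458)² = 20%

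For bias, monthly stopping is 3% after an uninjured report and 6% or 9% after an injured one. FAS odds ratios are given in that order:

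| True OR | Link in intervention arm only | Equal link | Link in control arm only |
|---|---|---|---|
| 1.00 | 0.89, 0.78 | 1.00, 1.00 | 1.13, 1.28 |
| 0.20 | 0.18, 0.17 | 0.21, 0.21 | 0.23, 0.26 |

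If stopping after March rises from 10% to 50% with injury equally in both arms, 0.20 becomes 0.23. The all-response fit stays at 1.00 or 0.20 throughout. That follows from the set-up, because stopping depends only on reported injuries.

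A separate simulation used gymnast SD 1.8, no club effect and 2% stopping when uninjured, and points the same way. At true OR 1.00 the FAS gave 0.99 when stopping after injury was 5% in both arms. It gave 0.85 with 5% in controls and 10% in the intervention arm, and 0.72 with 5% and 15%.

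**The case against.** The strongest reply concerns size. The SAP states no attrition, so every percentage follows from an assumed rate, and the larger ones are stress cases. Excluded gymnasts who dropped out hold only part of the eight months: at 2% monthly dropout, 9.6% of gymnasts go but only 3.8% of outcome months. That stands, which is why months and effective sample size are the better measures.

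On bias, the larger shifts under no effect need injury to triple the monthly stopping rate in one arm and not in the other. An equal link moves 0.20 only to 0.21 unless it is very strong. That also stands: with an equal link the cost is mostly precision.

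The comparison also favours the all-response fit, because no scenario lets stopping depend on unreported injury. There the wider set could be biased too. This limits the claim for the replacement but does not support discarding recorded outcomes.

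The second reading would lose nothing if everyone answered October. Under scattered non-response, however, it loses nearly as much as the first (0.9%, 3.6% and 8.3% at 10%, 20% and 30% missed), and it admits gymnasts without outcomes.

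Finally, the rule is pre-specified, is the same in both arms, and exclusions will be reported. That makes the loss visible without restoring the data.

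**Conclusion.** The concern holds. As written, the Publication I FAS removes gymnasts with valid outcome data on a condition met or failed after randomisation, and neither the per-protocol analysis nor the June-only model recovers those data. The mismatch itself rests on the SAP's text and needs no assumption about attrition.

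Its size does need one. Under 2% to 8% monthly dropout and the natural reading, 3.8% to 15.9% of outcome months and about 4% to 20% of effective sample size are lost. With scattered non-response of 10%, under 1% of outcome months are lost. Bias under no effect requires an injury–retention link that differs by arm, and it can go in either direction. Under a true effect an equal link can also shrink the estimate, usually only slightly. Nothing in the SAP shows that such a link exists. The definition should be changed because the risk is avoidable at almost no cost.

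**What to change.** In section 3.3, replace the Publication I response condition so that the FAS is all gymnasts randomised to either group with at least one OSTRC-H2 response from November 2022 to June 2023, analysed as randomised. Section 5.1 then applies unchanged. The per-protocol wording also needs no edit, since it is built on the FAS and takes over the new definition.

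Add one sentence keeping the present rule as a sensitivity set for the primary outcome, with its meaning bracketed: (October or November) and (at least one of April, May, June).

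The cost is one sentence replaced and one added; the same model is fitted to data already collected. The drawbacks are that some gymnasts contribute only a few months, and that the result still assumes non-response depends on reported injuries and not on unreported ones.
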